8.11 Arm 2- “Slow Pull”

The right or left lobe of the liver is initially targeted.

Doppler and EUS imaging are used to avoid significant vessels and large ducts when identifying appropriate biopsy tract.

The stylet is maintained from the onset of the procedure. It will later be used to push specimen through the needle. Using the 19g Acquire Boston Scientific needle, the needle is advanced into the liver just beyond the capsule. No fanning. The stylet is pulled back about 2cm. The needle is passed at least 4-5 cm into the liver with a quick forceful forward movement, as it is slowly withdrawn the nurse pulls back the stylet part with each withdrawal after actuation. This is repeated 2-4 times while the angle is changed slightly (1-3mm) with each actuation. The end the stylet is almost but not completely withdrawn from the needle. The needle is then pulled out of the liver. The needle is removed. The specimen is then taken for processing (see processing below).

The endoscopist then finds a second site to biopsy within the other lobe. If it is deemed by the endoscopist to not be able to biopsy the other lobe for technical reasons, this will be noted and tracked and an additional tract will be biopsied within the same lobe. Again, taking care to avoid vessels and large bile ducts, a second pass is made with the same technique.

In the event that a pass returns with no or inadequate tissue, the endoscopist will switch to the opposite technique and proceed as per protocol.

8.12 Total EUS time

Beginning of EUS examination which begins when the EUS scope is placed into the patient's mouth to when the EUS scope is withdrawn. EGD time prior to EUS is not counted. Room set up and anesthesia time is variable and not counted.

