8.9 EUS Guided Liver Biopsy

Upper endoscopy is performed with necessary biopsies or upper dilation completed if needed. Patients with evidence of significant upper gastrointestinal bleeding prior to endoscopy are exempt.

Once upper endoscopy is completed, the upper endoscope will be removed, and the Linear Array EUS scope is introduced per os. Diagnostic EUS examination is completed. EUS requiring pancreatic biopsies or interventions are exempt (See section 6). The patient is randomized to one of 2 techniques. The study will use block randomization stratified per site. The Randomization envelope is opened and the endoscopist is told which EUS guided liver biopsy technique is to be used.

Each technique will be used to perform 2 passes. A “pass” is defined as entry into the liver and then removal of tissue. An “actuation” is defined as a to and fro movement once the needle is within the liver.

An attempt to biopsy both left and right lobes of the liver will be made. If this cannot be completed for technical reasons, then the endoscopist will make a note and perform 2 passes to the lobe which is able to be biopsied.

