8.13 Total Liver Biopsy time

After completing the EUS examination including non-liver biopsies, the operator pays attention to the liver. The time starts for EUS liver biopsy. This should be the start time for the liver biopsy. The end time is then when the EUS scope is removed.

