12.2 Secondary Endpoints

- To identify complications within one week that are associated with each technique.
- To identify the time required for each step of the individual procedures.
- To identify additional findings of the procedure not related to liver disease.
- To identify any diagnostic differences in pathological findings between left and right liver lobe specimens

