12.3 Statistical Analysis

The two techniques will be compared for differences in fragmentation, total specimen length, and number portal tracts of the tissue using generalized linear mixed effects models (GLMM). The GLMMs will compare the two techniques while incorporating random effects for study site and endoscopist using the appropriate distribution and link function for each outcome (e.g. negative binomial distribution with log link for count data, binomial distribution with logit link for binary data). The GLMMs will also include a random effect to allow correlation between the two biopsy samples from each subject and a fixed effect to allow comparison between the two sides; an interaction between side and technique will be examined but removed from the model if not significant. Similar GLMM analyses will be performed for the comparisons of complications, technical success rate, total EUS time, total liver biopsy time, and recovery time. Analyses will be performed with sample processing technique included as a covariate in the analyses. Because of the small number of subjects with the mesh prep technique, the interaction between study group and sample processing technique will not be examined. Additionally, the analyses will be repeated after removing the subjects with the mesh prep technique. A 5% significance level will be used for all tests.

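### The timing endpoint promises a time for each step, but only three coarse clocks are defined, none isolates a step within the biopsy, and the liver biopsy clock has a subjective start

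*Combined protocol and SAP*

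**What the plan says.** Secondary objective 3.2b and the matching endpoint in 12.2 share one wording: "To identify the time required for each step of the individual procedures".

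Three clocks are defined:

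- **Total EUS time (8.12):** "Beginning of EUS examination which begins when the EUS scope is placed into the patient's mouth to when the EUS scope is withdrawn". The preceding upper endoscopy is left out: "EGD time prior to EUS is not counted".
- **Total liver biopsy time (8.13):** the start is described as "After completing the EUS examination including non-liver biopsies, the operator pays attention to the liver", and the stop as "The end time is then when the EUS scope is removed".
- **Recovery time (8.18):** from leaving the room to being ready for release.

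Section 12.3 analyses these three and no other times: "Similar GLMM analyses will be performed for the comparisons of complications, technical success rate, total EUS time, total liver biopsy time, and recovery time".

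On sequence, 8.9 first states "Diagnostic EUS examination is completed", then randomises, and then says "The Randomization envelope is opened and the endoscopist is told which EUS guided liver biopsy technique is to be used". Section 8.8 is looser. It permits opening at any point once consent and the eligibility checklist are done, and notes that this often happens after the patient has reached the procedure room.

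**The concern.** There are three linked problems.

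1. **The endpoint has no matching measurement.** A reader of 12.2 expects times for preparation, each pass and specimen handling, because those are the steps in which the two techniques differ. None is defined in section 8 or compared in 12.3.

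2. **The one technique-specific clock has a subjective start.** It begins when attention turns to the liver. That moment is set by an operator who may already know the arm. Arm 1 needs a needle flush and a loaded syringe, while Arm 2 keeps the stylet in place. Whether Arm 1's preparation is timed therefore depends partly on when the clock is called.

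3. **Total EUS time is a diluted copy of liver biopsy time.** The two share a stop event, so the larger clock only adds the diagnostic examination and any non-liver biopsies.

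At stake is whether the trial can say which technique is quicker, and at which step.

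**Working it through.** **Step 1: how the clocks relate.** Let T be total EUS time, L total liver biopsy time and D the interval from scope insertion to the start of the liver biopsy clock. T and L both stop when the EUS scope comes out (8.12, 8.13), so T = D + L. D contains the diagnostic EUS and any non-liver biopsies.

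**Step 2: which steps can be recovered.**

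- Diagnostic phase: yes, as T − L.
- Biopsy phase as a whole: yes, as L.
- Recovery: yes (8.18).
- Needle preparation, pass 1, pass 2, and expression of each specimen: no start or stop is defined.

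Under 8.14 the needle goes back to the endoscopist after the first specimen is expressed, so that expression falls inside L. Nothing ties scope removal to the second expression, which may fall outside.

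**Step 3: where Arm 1's preparation falls.** Section 8.10 lists targeting of the liver and Doppler first, then the flush and syringe attachment. Read in that order, preparation is inside L. Section 8.13 does not require that order, so preparation done earlier would fall outside.

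**Step 4: the plan's own power figure.** Section 11 uses a ratio of means of 1.2, a CV of 0.4, two-sided 5% and 80% power. On the log scale SD = √ln(1 + 0.4²) = 0.3853 and the difference is ln 1.2 = 0.1823. The normal formula gives 2 × 2.802² × 0.3853² / 0.1823² = 70.1, so 71 per arm. The t distribution gives 72, with 80.5% power. Then 72 / 0.9 = 80 enrolled per arm. The figure reproduces, but it concerns tract length and tract number, not times.

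**Step 5: sensitivity of T against L, in minutes.** Under the 8.9 order technique cannot change D, so T and L have the same expected arm difference. Var(T) = Var(L) + Var(D) + 2Cov(L, D). No SD for any time is given, so assume that L has exactly 80% power at 72 per arm. Put k = SD(D)/SD(L) and let ρ be the correlation of L and D. Power on T ≈ Φ(2.802/√(1 + k² + 2ρk) − 1.960).

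| k | Power on T, ρ = 0 |
|---|---|
| 0.25 | 78% |
| 0.5 | 71% |
| 1 | 51% |
| 1.5 | 34% |
| 2 | 24% |

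For example, at k = 1: 2.802/1.414 − 1.960 = 0.02, and Φ(0.02) = 51%. With ρ = 0, T needs 1 + k² times as many subjects to match L.

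At k = 1, power is 41% if ρ = +0.3 and 66% if ρ = −0.3. T beats L only if Cov(L, D) < −Var(D)/2. For example, ρ = −0.3 with k = 0.25 gives 83%.

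**Step 6: on a ratio scale.** A log link also shrinks the effect. If L is 20% longer in one arm and mean D is m times mean L, the ratio for T is (1.2 + m)/(1 + m): 1.13, 1.10 and 1.07 for m = 0.5, 1 and 2. Lognormal simulation (20,000 runs, CV 0.4 for both parts, 72 per arm, t-test on logs) gave power of 71%, 53% and 28%, against about 80% on L.

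**Step 7: if the arm is known before the diagnostic EUS.** D could then differ by arm. In the same kind of simulation, with no difference in L and D 10% longer in one arm, T was declared different in 18% of trials (m = 1) and 26% (m = 2), against a nominal 5%. The 10% is an assumption, chosen to show the direction.

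**The case against.** The strongest reply is that little is lost. Liver biopsy time is already compared separately in 12.3, and comparing total EUS time as well takes nothing from it. Total EUS time has objective start and stop events and describes the whole examination. With recovery time and the difference T − L, three phases are available, so rewording the objective would remove the mismatch. The CRF pages are not among the documents and may record more times. All of this stands, and it limits the weight of the point. It does not supply a definition or an analysis of any step within the biopsy.

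Three stronger readings are tempting, and the documents do not support them:

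- **Total EUS time adds only noise.** This needs the arm to be concealed until the diagnostic EUS is finished. Section 8.9 describes that order, but 8.8 does not guarantee it. With early opening the added part could carry bias.
- **A null result on total EUS time is to be expected even if one technique is clearly slower.** This depends on assumed values. With 72 per arm, liver biopsy SD 5 min and independent diagnostic SD of 5, 8 or 12 min, a 2.5-minute difference has 56%, 36% or 21% power on total EUS time (85% on liver biopsy time). A 5-minute difference has 99%, 89% or 64%. Excluding subjects who need pancreatic biopsies (6.2.10) also narrows the spread of the diagnostic phase.
- **The end of the liver biopsy clock is contaminated by other work.** No section describes other work between the second pass and scope removal. Non-liver biopsies come before the clock starts.

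**Conclusion.** The point holds in a limited form. As written, the plan cannot deliver step times within the biopsy, and this conclusion needs no numerical assumption. The subjective start of liver biopsy time is a real weakness, although the written order in 8.10 suggests that Arm 1's preparation is counted.

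Total EUS time will usually be the less sensitive technique comparison. The size of the loss is not known from the documents. Across the assumed SD ratios 0.25 to 2 with independent phases, 80% power falls to between 78% and 24%, and a negative correlation can reduce or remove the loss. Whether the added phase brings noise alone or bias as well depends on when the envelope is opened, on which 8.8 and 8.9 do not agree.

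These are secondary endpoints. The sample size does not rest on them, and the primary conclusion is unaffected. The change is still worth making, because it is cheap and lets the trial answer a question that it sets itself.

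**What to change.** 1. **8.13:** start total liver biopsy time at an observable event, with the same rule in both arms, for example the start of needle preparation or the first needle entry. If needle entry is chosen, stamp the start of preparation separately.
2. **Procedure CRF:** record needle entry and exit and the end of specimen expression for each pass. Where the technique is switched after a failed pass, per-pass times also keep the two techniques apart.
3. **12.3:** add these step times to the technique comparisons, make total liver biopsy time the main timing comparison, and state that total EUS time is interpreted descriptively.
4. **8.8 and 8.9:** reconcile when the envelope is opened, and record the opening time.
5. **3.2b and 12.2:** for subjects already enrolled, limit the objective to the phases measured (diagnostic, biopsy, recovery).

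The cost is a few more CRF fields for the nurse and edits to the sections named, with no extra staff. Subjects already enrolled will have only the old totals, so step times will rest on a subset.

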8.13 Total Liver Biopsy time

After completing the EUS examination including non-liver biopsies, the operator pays attention to the liver. The time starts for EUS liver biopsy. This should be the start time for the liver biopsy. The end time is then when the EUS scope is removed.

8.14 Specimen Processing within Surgical Suite

After completion of each pass, the specimen is processed by the technician or nurse:

- Process as surgical specimen – histologic sample in 10% formalin
- Caution should be used to avoid fragmentation of specimens
- **ARM 1:** A specimen (in the modified wet suction technique) should not come into the chamber of the suction syringe. If this should happen, remove the plunger from the syringe to limit fragmentation and pour contents into the specimen jar. Assuming that the specimen does not go into the syringe, use the stylet to slowly push the specimen out. As the specimen touches the formalin the capillary pull of the formalin will help to withdraw the tissue. Once the specimen makes contact with the formalin slowly swirl the specimen in an outward circle around the jar. The swirling and gentle expression avoids fragmentation
- After expression of specimen, the needle is flushed with 10 – 20 cc of saline. Any additional tissue from this flush should also be captured in the specimen jar.
- The needle is taken back to the endoscopist for second pass or discarded if both passes have been completed and the procedure is over.
- Repeat the above specimen prep for the second pass.
- Specimens should be labeled according to the lobe of acquisition.
- **ARM 2:** For slow pull technique, the stylet can be used to express the specimen slowly ensuring that it remains intact. Use the same technique of capillary pull and swirling to avoid fragmentation.
- After expression of specimen, the needle is flushed with 10 – 20 cc of saline. Any additional tissue from this flush should also be captured in the specimen jar.
- The needle is taken back to the endoscopist for second pass or discarded if both passes have been completed and the procedure is over.
- Repeat the above specimen prep for the second pass
- Specimens should be labeled according to the lobe of acquisition.

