8.10 Arm 1- “Modified Wet suction”

The right or left lobe of the liver is initially targeted.

Doppler and EUS imaging are used to avoid significant vessels and large ducts when identifying appropriate biopsy tract.

The stylet is removed from the onset of the procedure. It will only be used to push the specimen out of the needle. A syringe is used to flush the needle with 5 cc of saline. Then a syringe that contains 3cc of saline with preloaded 20cc of suction with the valve in the off position is attached to the back of a 19g Acquire Boston Scientific needle. The needle is advanced into the liver just beyond the capsule. An initial pass of at least 4-5 cm is made into the liver with a quick forceful forward movement, the needle is then slowly pulled back to the edge of the capsule. The valve is switched to the open position. 2-4 actuations are made driving the needle at least 4-5 cm in length every time while the angle is changes slightly (1-3mm) with each actuation. No fanning. The needle is then pulled out of the liver with the valve switched to the closed position just prior to removing the needle from the liver. Often a flash of blood may be seen. The needle is removed and the specimen is taken for processing (see processing below).

The endoscopist then finds a second site to biopsy within the other lobe. If it is deemed by the endoscopist to not be able to biopsy the other lobe for technical reasons, this will be noted and tracked and an additional tract will be biopsied within the same lobe. Again, taking care to avoid vessels and large bile ducts, a second pass is made with the same technique.

In the event that a pass returns with no or inadequate tissue, the endoscopist will switch to the opposite technique and proceed as per protocol.

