8.16 Post Biopsy CRF

A summary of lobes biopsied, pathology findings, EUS findings and EGD findings.

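### The left-right comparison can partly reflect pass order: the first lobe is uncontrolled, jars are labelled by lobe, and the model has side but no pass term

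*Combined protocol and SAP*

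**What the plan says.** - **Order of lobes.** Sections 8.10 and 8.11 both state "The right or left lobe of the liver is initially targeted", and for the second pass "The endoscopist then finds a second site to biopsy within the other lobe". No section fixes, alternates or randomises the first lobe. The documents do not say outright who picks it; without a rule, the choice falls to the operator.
- **What is randomised.** Only technique. Under Section 8.9 the arm is known before the liver is targeted: "The Randomization envelope is opened and the endoscopist is told which EUS guided liver biopsy technique is to be used".
- **Exceptions.** If one lobe cannot be reached, both passes go to the same lobe (8.9). After a pass with no or inadequate tissue, the operator changes to the other technique (8.10, 8.11).
- **Specimen identity.** Section 8.14 says "Specimens should be labeled according to the lobe of acquisition", and Appendix A repeats it. Neither asks for a pass number. The post-biopsy form is described in Section 8.16 as "A summary of lobes biopsied, pathology findings, EUS findings and EGD findings".
- **Needle.** The same needle is flushed and reused: "The needle is taken back to the endoscopist for second pass" (8.14).
- **Model.** Section 12.3 plans GLMMs with a random effect linking a subject's two specimens, "a fixed effect to allow comparison between the two sides", and a side-by-technique interaction that is dropped if not significant. It has no pass term. Left versus right is a secondary objective (3.2) and endpoint (12.2).

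**The concern.** When both lobes are sampled, lobe and pass number coincide within each subject: one lobe is pass 1 and the other is pass 2. The two effects separate only because some subjects start left and others right, and only if the analysis knows which. The planned model does not use that information, and the specified label does not record it. If operators tend to start in the same lobe and the second pass yields more or less tissue than the first, the side coefficient estimates lobe plus a share of the order effect.

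An order effect is plausible, because the needle is reused and a poor first pass changes the technique. At stake are the left-right yield comparison and the side-by-technique interaction. There is also a narrower traceability question. If both passes come from one lobe and the technique was switched, two jars carry the same label, and that label does not show which technique produced which specimen.

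**Working it through.** **The plan's own figure.** Section 11.0 gives 72 completers per group for a ratio of means of 1.2, CV 0.4, two-sided 5% and 80% power. On the log scale, SD = sqrt(ln(1 + 0.4²)) = 0.385 and difference = ln(1.2) = 0.182. The normal approximation gives 71 per group; the noncentral t gives 72, with power 80.5%. Then 72/0.9 = 80 per group, 160 in total. The figure reproduces, and this point does not alter it.

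**Inputs for the check.** From the plan: N = 144 and CV 0.4, applied here to the single specimen. Assumed: both lobes sampled in every subject; within-subject correlation 0.5; f, the share starting left; r, the pass-2/pass-1 yield ratio; no true lobe difference.

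**Bias.** A left-first subject contributes ln r to the right-minus-left log difference, and a right-first subject contributes -ln r. The mean is (2f - 1) × ln r.

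**Standard error.** SE = 0.385 × sqrt(2 × (1 - 0.5))/sqrt(144) = 0.0321. If the mixed starting order is left in the residual, the variance of a subject's difference rises by 4f(1 - f)(ln r)².

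- *f = 0.8, r = 0.85:* 0.6 × (-0.1625) = -0.0975, ratio 0.91. z = 0.0975/0.0321 = 3.04, so 86% of trials are significant. With the extra variance, SE = sqrt(0.1484 + 0.64 × 0.0264)/12 = 0.0339, z = 2.88, 82%.
- *f = 0.7, r = 0.90:* 0.4 × (-0.1054) = -0.0421, ratio 0.96. z = 1.31, 26%; with the extra variance, about 25%.

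**Range.** The false left/right ratio, and the rejection rate of a nominal 5% test with the extra variance included, for pass-1/pass-2 yield ratios of 1.1 and 1.2:

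| Share starting left | Ratio 1.1 | Ratio 1.2 |
|---|---|---|
| 0.5 | 1.00, 5% | 1.00, 5% |
| 0.6 | 1.02, 9% | 1.04, 18% |
| 0.7 | 1.04, 21% | 1.08, 55% |
| 0.8 | 1.06, 42% | 1.12, 89% |
| 0.9 | 1.08, 65% | 1.16, 99% |
| 1.0 | 1.10, 84% | 1.20, 100% |

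At f = 0.8, moving the correlation from 0.3 to 0.7 moves the rejection rate from 32% to 61% (ratio 1.1) and from 78% to 98% (ratio 1.2). Simulation with 4,000 trials per setting agrees for f = 0.5 to 0.9; at f = 0.8 it gives 40% and 88%.

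**Interaction.** With shares f1, f2 and pass ratios r1, r2 in the two arms, the spurious interaction is (2f1 - 1) ln r1 - (2f2 - 1) ln r2. It can be non-zero when the arms differ in starting lobe, which is possible because the operator knows the arm, or in order effect.

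**Between-arm comparison.** Each subject is planned to give one pass 1 and one pass 2, so a common order effect enters both arms equally and cancels.

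**With pass in the model.** Simulated type I error for side is 4.5% to 5.5% for f = 0.5 to 0.9. The variance of the side estimate is multiplied by 1/(4f(1 - f)): 1.04 at f = 0.6, 1.19 at 0.7, 1.56 at 0.8, 2.78 at 0.9. For a true 10% lobe difference at f = 0.8, z falls from 0.1054/0.0321 = 3.28 (power about 91%) to 3.28/sqrt(1.56) = 2.63 (about 75%).

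**The case against.** The best defence is that neither ingredient of the bias is documented. No passage reports a left-first habit or a lower yield on pass 2, and the needle is flushed between passes. With even starts or no order effect nothing is wrong, and the milder case gives only a 4% spurious difference. All of this stands, so the size is conditional. It does not remove the gap: the plan secures neither condition, and the specified data would not let anyone check.

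Four stronger readings are tempting, and the documents do not support them.

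- *A reader might infer that the primary comparison is confounded, since side sits in every primary model.* Technique is randomised by subject and both arms have the same two-pass structure, so it is largely protected. The exception is the switched, same-lobe case.
- *A reader might infer that specimens cannot be traced to their technique.* The case report forms are not shown, specimens are processed after each pass, and failure to reach the second lobe is recorded. The documents show only that no pass identifier is specified.
- *A reader might infer that lobe and order can never be separated.* They can, if starts are mixed and pass is recorded and modelled.
- *A reader might extend the figures to the secondary endpoint as worded, which concerns diagnostic findings.* The calculation covers tissue yield only; nothing here shows that pass order changes a diagnosis.

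**Conclusion.** The point holds for the side effect on tissue yield and for the side-by-technique interaction: as planned, each can partly reflect pass order. The size depends on two unknowns, the imbalance in first lobe and the pass effect. It runs from nothing to complete confounding if every subject starts in the same lobe. The illustrative cases further rest on an assumed correlation of 0.5 and on both lobes being sampled in all 144 subjects. The sample size and the overall comparison of techniques stand, apart from the labelling ambiguity for subjects with both passes in one lobe and a change of technique. This is a cheap improvement to a secondary comparison, not a flaw in the main result.

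**What to change.** 1. Label each jar with lobe and pass number only. Technique must not go on the jar: the pathologist who scores fragmentation, length and portal tracts is to stay blinded to it (8.15, Appendix A).
2. Record first lobe, pass number and technique actually used for each pass on a procedure form that the pathologist does not see.
3. In Section 12.3, add pass number as a fixed effect alongside side, and report the share of subjects starting in each lobe.
4. State in advance that if every operator starts in the same lobe, the side result will be reported as lobe plus order, since modelling cannot separate the two in subjects with both lobes sampled.

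The administrative cost is a label entry, a few form fields and one model term, with no change to the 160 subjects. The statistical cost is collinearity rather than degrees of freedom: the side estimate loses precision by the variance factors shown above, more so as starts become more one-sided. That loss reflects how little the data can say about lobe apart from order.
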